11.5.2.4.3 WAZ adjusted for gestational age

For a sensitivity analysis WAZ is adjusted for gestational age by using the following age calculation:

$$Age_{GA}(weeks) = Age(weeks) - (37 - GA(weeks))$$

where:

- Age (weeks) is calculated as age (days)/7 and rounded down to closest integer,
- GA(weeks) is reported gestational age in weeks.

WAZ_{GA} is re-calculated using Age_{GA} (days) which is calculated as Age_{GA}(weeks) multiplied by 7 and rounded down to closes day.

 WAZ_{GA} will be summarized similarly to WAZ by treatment and visit. A listing will be included with actual and CFB values for WAZ_{GA} . Summaries for WAZ_{GA} will not be presented for any subgroup.

Finally, the same model used in Section 11.5.2.1 is run using CFB in WAZ_{GA} at Day 56 visit as outcome, and baseline WAZ_{GA} and Age_{GA} (days) as covariates in the model instead of WAZ and Age (days). The same summary table will be presented for WAZ_{GA} for the mITT population.

Missing gestational age will not be imputed.

11.5.3 Key Secondary Outcome: CFB in Weight (grams) at Day 56

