8.1. Demographic and Baseline Characteristics

The following information pertaining to the participant will be obtained from the participant's mother at screening:

- Participant's sex, race, ethnicity, date of birth (including day, month, and year), and whether the delivery was a C-section.
- Participant's gestational age in weeks, if known, and the participant's birth weight (in kilograms). This information may be obtained from the hospital medical record if necessary.
- The mother's age will be obtained whenever possible.
- The participant's mother will be asked about breast-feeding practices from the time of the participant's birth, and planned feeding practices during the study (and this information will be captured in the case report form).

A full medical history and full physical examination will be performed at the screening visit (refer to Section 8.3.1). The participant's anthropometric measurements will be taken at the screening visit and at other specified timepoints in the SoA (refer to Table 2 and Section 8.3.1) for more details).

If the eligibility criteria are met, the participant will be enrolled into the study on Day 1. After enrollment, an estimation of socioeconomic status will be obtained if possible.

Hospital discharge to home, or to nutritional rehabilitation unit, will be collected on Day 1 and obtained from either the participant's parent(s)/legal guardian, or the hospital medical record. The anthropometric measurements obtained at Day 1 will be considered baseline for the purposes of statistical analyses (refer to Section 9.2).

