10 OVERALL STATISTICAL CONSIDERATIONS

10.1 General Conventions

Descriptive statistics will be presented for continuous data with applicable decimal precision as follows in relation to the source data (indicated as N+x), with a maximum of 3 decimals to be displayed:

- Number (N).
- Mean, (N+1).
- Number of missing observations, (N).
- Standard deviation (SD), (N+1).
- Median, (N+1).
- Minimum, (N+1).
- Maximum, (N+1).

Absolute and relative frequencies will be used to describe categorical variables. Unless otherwise specified, the denominators for percentages will be the number of participants in each intervention group with non-missing data for the variable of interest at the summarized visit. Percentages will be presented with 1 decimal place and a percent sign (%).

All statistical testing will be 2-sided and performed at the 0.05 level. When reporting the results of significance tests p-values will be reported. All confidence intervals will be 2-sided at the 95% level, unless otherwise stated.

Study day is calculated relative to the first study intervention administration on Day 1.

Confidential Page 22 of 50

- If the current ACR date is after study intervention administration: Study Day = (Current ACR Date – Study Intervention administration Date) + 1
- If the current ACR date is before study intervention administration:

Study Day = (Current ACR Date – Study Intervention administration Date)

Study day will not be calculated if either the current ACR or the study intervention administration date is incomplete or missing.

The following periods for the study are defined:

- Treatment Period: Day 1 through last dose of participant.
- Follow-up Period: Day of last dose of participant + 1 up to EoS.

SAS® code of SAS® procedures that will be used to perform efficacy and safety analyses is provided in Appendix 3.

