10.6 Visit Windows/Unscheduled Visits

Data at each visit are to be captured within the following windows for each of the intended visits:

Table 4. Visit windows

Visit name	Visit window	
Screening	≤ 7 days before randomization	
Randomization	Day of hospital discharge, Day 1	
Clinic Visit 1	Day 1	
Home Visits at Week 1	Within ± 1 day of Day 7, ie, Days 6-8	
Home Visit at Week 2	Within ± 1 day of Day 14, ie, Days 13-15	
Home Visit at Week 3	Within ± 1 day of Day 21, ie, Days 20-22	
Clinic Visit 2	Within ± 1 day of Day 28, ie, Days 27-29	
Home Visit at Week 5	Within \pm 2 days of Day 35, ie, Days 33-37	
Home Visit at Week 6	Within \pm 2 days of Day 42, ie, Days 40-44	
Home Visit at Week 7	Within ± 2 days of Day 49, ie, Days 47-51	
Clinic Visit 3	Within ± 2 days of Day 56, ie, Days 54-58	
Clinic Visit 4	Within \pm 2 days of Day 90, ie, Days 88-92	

Additional visit windowing will not be applied. Unscheduled visits will not be included in by-visit summary tables or analysis but may contribute to the Baseline value and listed in by-participant data listings. In the case of a retest (same visit number assigned), the latest available test result as provided in the data transfer for that visit/time point will be used for by-visit summaries.

Confidential Page 24 of 50

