11.5 Efficacy

11.5.1 Calculation of Weight-for-age z-score

WAZ is calculated at Screening and all clinical visits (Days 1, 28, 56, and 90).

The WAZ score is calculated in EDC using the approach defined by the WHO [2]. Given the weight (kg), sex and age (in days) of a participant, the WAZ is calculated as

Confidential Page 31 of 50

$$WAZ = \frac{\left(\left(\frac{Weight}{M}\right)^{L} - 1\right)}{L \times S}$$

where L, M, and S are pre-derived parameter estimates generated by the WHO. L, M, and S are conditional on the Sex and Age (days) of the infant. The lookup tables for the values of L, M, and S can be found on the WHO website [2]. Distinct tables for males and females are given.

WAZ is calculated directly in EDC and need not be derived. WAZ is rounded off to 2 decimals. The value for WAZ (at enrollment) after rounding off is used for randomization and defining the strata $(-3 < \text{WAZ} < -2, \text{WAZ} \le -3)$ (also used for study eligibility).

11.5.2 Primary outcome: CFB in WAZ at Day 56

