11.5.2.1 Analysis of endpoint

WAZ will be summarized using descriptive statistics for actual and CFB values by visit and treatment group.

A MMRM will be used to estimate the difference in mean CFB between Bi-26 and Placebo, adjusting for covariates baseline WAZ, age (in days), country and discharge destination. The model will use CFB in WAZ as outcome and include the following effects:

- Fixed effects: Treatment, Visit (categorical), Treatment*Visit interaction, WAZ at baseline (continuous), Age (in days) at baseline, Country, Discharge destination
- Random intercepts: participant.

and will be fit using data from all planned follow-up visits where WAZ was measured, ie, Day 28, 56, and 90 visits. The adjusted interaction effects (Treatment*Visit) will be presented as estimates of the difference in CFB between treatment groups at each follow-up visit (Day 28, 56, and 90). The associated 95% CIs and p-values will be presented. PROC MIXED will be used to fit the models. SAS code for the models is provided in Appendix 3. If the WAZ score is not normally distributed, an appropriate transformation, such as the natural log, will be used as outcome for analysis. Normality will be investigated using q-q plots.

A participant listing of WAZ will be presented with actual values and CFB.

The descriptive table, model and listing will use the mITT population. The summary table will be repeated for the PP population.

Line graphs with the means and 95% CIs for WAZ will be presented by treatment group for visits Baseline, 28, 56, and 90.

Confidential Page 32 of 50

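### The gestational-age-adjusted WAZ sensitivity analysis rounds age down to whole weeks although WAZ is indexed by day, which adds small, avoidable noise to the change score

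*SAP*

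**What the plan says.** SAP 11.5.2.4.3 defines the adjusted age by "Age_{GA}(weeks) = Age(weeks) - (37 - GA(weeks" (closing brackets follow). The age that enters the formula is coarsened first: "Age (weeks) is calculated as age (days)/7 and rounded down to closest integer". The adjusted weeks are multiplied by 7, rounded down to the day and used to recalculate WAZ. The result, WAZ_GA, "will be summarized similarly to WAZ by treatment and visit". The primary model is then re-run with change from baseline in WAZ_GA at Day 56 as outcome, and with baseline WAZ_GA and adjusted age in days as covariates.

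SAP 11.5.1, which defines WAZ itself, works in days: "L, M, and S are conditional on the Sex and Age (days) of the infant".

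The model being re-run (SAP 11.5.2.1) "will be fit using data from all planned follow-up visits where WAZ was measured, ie, Day 28, 56, and 90 visits". The Day 56 window in SAP 10.6 is "2 days of Day 56, ie, Days 54-58". Protocol 8.1 collects "gestational age in weeks, if known".

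**The concern.** A GA sensitivity analysis should differ from the primary analysis only through the GA correction. Here a second change comes with it. Day-level age is available and is used for the primary WAZ, but it is dropped before the correction is applied. An infant of GA 37 weeks should have WAZ_GA equal to WAZ, yet is scored up to 6 days too young.

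The number of days lost can also differ between two visits of the same infant. Every scored interval becomes a multiple of 7 days, although the true interval to nominal Day 56 is 55 days. The outcome is a change score, so an error in the interval feeds into it directly. At stake is the precision of this one analysis, and whether a difference from the primary result can be read as an effect of GA alone.

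**Working it through.** The SAP states no numerical result for this analysis, so there is no figure to reproduce. The rule can be enumerated in full.

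**Inputs**
- Enrollment age a = 30 to 120 days, which is 91 whole-day ages (Protocol 5.1).
- Day 1 is the first dose, so day d is d - 1 elapsed days (SAP 10.1).
- Day 56 window: Days 54 to 58 (SAP 10.6).
- GA in whole weeks (SAP 11.5.2.4.3).
- Planning SD of the WAZ change: 1.3 (Protocol 9.4, SAP 7.1.3).

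**Age at one visit.** As printed, the adjusted age in days is 7 x (floor(age/7) - (37 - GA)). In days it would be age - 7 x (37 - GA). The difference is age mod 7, whatever the GA. Since 91 = 7 x 13, each value from 0 to 6 occurs for 13 enrollment ages. The mean loss is (0+1+2+3+4+5+6)/7 = 3 days.

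**Interval from baseline to day d.** As printed: 7 x (floor((a + d - 1)/7) - floor(a/7)). True: d - 1. GA cancels.

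Two infants of GA 37 seen exactly on Day 56 show the effect:
- Enrolled at 34 days: scored at 28 days, then at 84 (true age 89). Interval 56 days, error +1.
- Enrolled at 35 days: scored at 35 days, then at 84 (true age 90). Interval 49 days, error -6.

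All 91 ages across the window:

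| Visit day | True interval | Interval error in days (number of ages) | Mean | Variance |
|---|---|---|---|---|
| 54 | 53 | +3 (52), -4 (39) | 0 | 12 |
| 55 | 54 | +2 (65), -5 (26) | 0 | 10 |
| 56 | 55 | +1 (78), -6 (13) | 0 | 6 |
| 57 | 56 | 0 (91) | 0 | 0 |
| 58 | 57 | -1 (78), +6 (13) | 0 | 6 |

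For Day 56 the variance is (78 x 1 + 13 x 36)/91 = 546/91 = 6, an SD of 2.45 days. These are counts of possible ages, not of infants. Nominal Day 28 (true interval 27 days) behaves like nominal Day 56: +1 for 78 ages and -6 for 13. At nominal Day 90 (true interval 89 days) the error is +2 for 65 ages and -5 for 26. With age kept in days, the error is 0 at every age, visit day and GA.

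**Size in z-scores.** The documents do not give the WHO parameters, so the change in WAZ per day of age is an assumption: 0.03 to 0.07, taken as equal at both visits. For the largest interval error, 6 x 0.03 = 0.18 to 6 x 0.07 = 0.42 WAZ for that infant. The added variance at nominal Day 56, against 1.3 squared = 1.69, is:
- 6 x 0.03² / 1.69 = 0.0054/1.69 = 0.3%
- 6 x 0.07² / 1.69 = 0.0294/1.69 = 1.7%

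Day 54, the least favorable day in the window, has twice the variance and so gives about 0.6% to 3.5%.

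**GA above 37 weeks.** The printed formula subtracts a negative number. Before rounding, age rises by 7 x (GA - 37): +7 days at GA 38, +21 at GA 40, +35 at GA 42.

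**The case against.** The strongest defense is that the rule is complete, reproducible and identical in both arms. GA is recorded only in weeks, and Protocol 4.2 expects that an accurate value will often be unknown, so working in whole weeks may look consistent with the data. At nominal Day 56, 78 of 91 ages are off by only one day.

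The point about size stands, and it is why this is minor. The point about GA precision does not. An error in GA shifts an infant's age by the same amount at every visit and leaves the interval at its true length. Rounding age down changes the interval, so it adds a separate error without reducing the first.

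A reader might go further in three ways that the documents do not support:
- **That the treatment comparison is biased, or the primary result is touched.** The primary WAZ uses age in days. The rounding does not depend on arm, and the mean interval error is zero with ages weighted equally.
- **That the SAP leaves open what happens when GA exceeds 37 weeks.** The formula settles it: age goes up. Only the intention is unstated. A common 37-week reference for all infants is a possible reading, and no text limits the correction to preterm infants, so a cap cannot be called the right rule.
- **That negative adjusted ages undermine the analysis.** They are possible on Day 1 (at GA 32 weeks, for enrollment ages 30 to 34 days) and no rule is given. That is a missing detail at low GA and young age, not a further error in the formula.

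**Conclusion.** The point holds as a minor error of specification. Rounding age to whole weeks makes the adjusted age 0 to 6 days too low. At nominal Day 56 the scored interval is 56 days for 78 of 91 enrollment ages and 49 days for 13, against a true 55; across Days 54 to 58 the error runs from -6 to +6 days.

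The effect is noise in one sensitivity analysis, and it is probably small: about 0.3% to 1.7% of the planning variance at nominal Day 56. That range rests on the assumed 0.03 to 0.07 WAZ per day, on the same slope at both visits, and on equal weighting of enrollment ages. The day counts need only the SAP's own rule and whole-week GA. The documents do not give the GA distribution, so the number of infants affected cannot be stated.

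**What to change.** In SAP 11.5.2.4.3, replace the two-step calculation with Age_GA(days) = Age(days) - 7 x (37 - GA(weeks)). Drop the rounding to weeks and keep only the existing rounding down to the day. An infant of GA 37 weeks then has WAZ_GA equal to WAZ, and every interval keeps its true length.

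As a minor clarification, add one sentence saying whether GA above 37 weeks is meant to raise age (for example by 21 days at GA 40). Add a cap, replacing 37 - GA with max(0, 37 - GA), only if the sponsor means to adjust preterm infants alone.

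The cost is one changed formula and one sentence. No new data are needed.

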4.2. Scientific Rationale for Study Design

Gut dysbiosis, or disrupted development of the gut microbiota, is hypothesized to be a contributing cause of infant malnutrition. Absolute *B. infantis* abundance is reported to be markedly lower in 3-to-24-month-old Bangladeshi infants and children under 24 months of age with SAM, compared to their healthy controls. The primary hypothesis to be tested in this study is Bi-26 supplementation for 28 days will lead to increased weight gain in underweight infants (WAZ <-2) who were hospitalized with acute non-surgical illness.

This study is designed as a double-blind, placebo-controlled study to enable equal attention and an unbiased evaluation of AEs and health outcomes.

WAZ was selected as the primary endpoint because it appears to be a better surrogate for mortality than WLZ [Mwangome 2019; Chowdhury 2021]. However, weight-for-age Z-scores require that the birth date of the infants enrolled is known and that weight is determined accurately.

We anticipate that an accurate gestational age at birth will often not be known for the infants enrolled. The study population will be heterogeneous and will include prematurely born infants and infants with normal weight-for-gestational age, infants with intrauterine growth retardation born small-for-gestational age, and infants with insufficient postnatal weight gain or weight loss due to illness and/or undernutrition.

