5.1. Inclusion Criteria

Participants are eligible to be included in the study only if all of the following criteria apply:

Age

1. Participant must be between 30 days and 120 days of age (inclusive), at the time of enrollment (study Day 1)

Type of Participant and Disease Characteristics

- 2. Hospitalized for acute non-surgical illness
- 3. Completed acute stabilization phase of treatment, including fluid rehydration and antibiotic course, prior to enrollment (study Day 1)

Weight

4. WAZ at enrollment (study Day 1) is less than negative 2 (<-2)

Sex

5. Any

Informed consent

6. Participant's parent(s)/legal guardian is capable of giving informed consent which includes agreement to comply with the requirements and restrictions listed in the informed consent form (ICF) and in this protocol

Additional requirements

- 7. Participant's parent(s)/legal guardian agrees to stay in contact with the study site for the duration of the study, provide updated contact information as necessary, and have no current plans to relocate from the study area for the duration of the study
- 8. Participant's parent(s)/legal guardian has easy access to reliable refrigeration (for storage of investigational product)
- 9. Participant receives some feedings from breastmilk and mother intends to continue breast-feeding.

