10.3.3 Missing Efficacy data

Missing efficacy data will not be imputed.

Confidential Page 23 of 50

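### The gestational-age sensitivity analysis changes both the age used for WAZ and the set of infants, with no run that separates the two and no rule for a negative corrected age

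*SAP*

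**What the plan says.** SAP 11.5.2.4.3 defines corrected age in weeks as age in weeks minus (37 minus GA in weeks), using the reported GA. On rounding it says: "Age (weeks) is calculated as age (days)/7 and rounded down to closest integer". The result is multiplied by 7 to give days, and WAZ is recalculated at that age. Then "the same model used in Section 11.5.2.1 is run using CFB in" the corrected WAZ, with corrected baseline WAZ and corrected age replacing the original covariates. The population is given as mITT. The section ends: "Missing gestational age will not be imputed". This agrees with the general rule in SAP 10.3.3: "Missing efficacy data will not be imputed". Table 8 in Appendix 3 lists the analysis as mITT, MMRM, observed cases.

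Protocol 8.1 collects GA at screening from the mother, or from the hospital record if necessary, and only where it is known. Protocol 4.2 adds: "We anticipate that an accurate gestational age at birth will often not be known for the infants enrolled". The same section expects prematurely born infants in the study. Protocol 5.1 admits infants from 30 to 120 days of age, and neither 5.1 nor 5.2 sets a lower limit on GA.

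**The concern.** The analysis is meant to show whether the primary result survives correction for prematurity. An infant without a reported GA has no corrected WAZ, corrected baseline or corrected age, and so cannot enter the model. The mITT label, shared with the primary analysis, suggests the same infants in both; the two sets will differ by however many lack GA. A gap between the two estimates could then come from the age correction, from the selection of infants whose GA was recorded, or from the noise of a smaller sample. A reader could take a weaker corrected estimate as dependence on prematurity, or a similar one as reassurance, and neither conclusion would be secure.

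Separately, subtracting the weeks of prematurity from a short postnatal age can give a value below zero on Day 1. The SAP does not say what happens then.

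**Working it through.** **1. Is a same-infant comparator planned?** SAP 11.5.2.4.1 repeats the model in the PP population. SAP 11.5.2.4.2 adds possible confounders, and GA is not among them. The subgroup list in SAP 8.2 has no GA-known group; its allowance for other subgroups is not a pre-specified comparator. Table 8 has no such row. So no uncorrected run in the GA-known infants is planned.

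**2. When is the corrected age negative?** Inputs: the SAP 11.5.2.4.3 formula and the entry ages in Protocol 5.1. Corrected Day 1 age in days = 7 × [floor(age/7) − (37 − GA)], which is negative when floor(age/7) < 37 − GA.

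| Day 1 age (days) | Completed weeks | Negative for GA (weeks) | Example |
|---|---|---|---|
| 30-34 | 4 | 32 or less | GA 32: 4 − 5 = −1 week |
| 35-41 | 5 | 31 or less | GA 31: 5 − 6 = −1 week |
| 42-48 | 6 | 30 or less | GA 30: 6 − 7 = −1 week |
| 49-55 | 7 | 29 or less | GA 29: 7 − 8 = −1 week |
| 56-62 | 8 | 28 or less | GA 28: 8 − 9 = −1 week |

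Rounding is not the cause: unrounded, GA 32 at 30 days gives 30 − 35 = −5 days. By the Day 56 visit (age plus 55 days) no infant with GA 25 or more is negative: 30 + 55 = 85 days is 12 completed weeks, and 12 − (37 − 25) = 0. For those infants it is the baseline that would fail, and with it the change score at every visit.

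**3. How far could the two estimates differ by chance?** Inputs from SAP 7.1.3: difference 0.45, SD 1.3, two-sided 5%, power at least 90%, 177 per group. The plan's figure reproduces: the noncentral t calculation gives power 0.901 at 177 per group and 0.899 at 176.

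Full-sample SE = 1.3 × √(2/177) = 0.138.

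The share f with reported GA is not in the documents, so it is an assumption. For a subset nested in the full sample, with the same true effect and no age correction, SD(subset − full) = √(SE_subset² − SE_full²) = SE_full × √(1/f − 1). The 95% range is ±1.96 times this.

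| f | n per arm | SE in subset | SD of difference | 95% range (WAZ) | Range / 0.45 |
|---|---|---|---|---|---|
| 80% | 142 | 0.154 | 0.069 | ±0.135 | 30% |
| 70% | 124 | 0.165 | 0.090 | ±0.177 | 39% |
| 60% | 106 | 0.178 | 0.113 | ±0.221 | 49% |
| 50% | 88 | 0.195 | 0.138 | ±0.271 | 60% |

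**4. Does whole-week rounding matter to the comparison?** Yes. Over a true 55-day interval the corrected age advances 56 days for 78 of the 91 possible entry ages and 49 days for the other 13. Even at GA 37, where the correction is zero, rounding lowers Day 1 age by 0 to 6 days (mean 3.0 over those entry ages). A same-infant comparison that kept the rounding would still mix two causes.

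**The case against.** - **Frequency.** A reader might infer that the protocol expects GA to be missing often. Protocol 4.2 speaks of an accurate GA, while the SAP uses the reported one, and an inaccurate report still enters the model. Recording GA only where known makes some missing values likely, but the documents do not say how many. This stands.
- **Failure.** The subset has less power (about 0.63 at 50% availability and 0.83 at 80%), and one might call the shortfall a failure rate. The SAP sets no pass/fail rule here; it reports an estimate with a 95% CI, whose width will show the lost precision. This stands.
- **Model.** The planned model adjusts for covariates and uses three visits, so the figures above are not its standard errors. This stands; they indicate scale only.
- **Negative ages.** It is tempting to conclude that the infants most in need of correction will be lost. That assumes a growth table starting at age 0, which the documents do not state. The number is also unknown and probably small, because exclusion criterion 2 requires discharge and at least a week at home since birth. That criterion does not rule out GA 32 at 30-34 days, so the missing rule remains a gap.
- **Bias.** GA is fixed before randomization, so Bi-26 versus placebo within the subset remains a randomized comparison. This stands.
- **Existing reporting.** SAP 11.2 shows the number with missing GA, and SAP 10.1 requires counts of missing observations in summaries. Total loss by arm will be visible. That does not separate the age correction from the change of sample.

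**Conclusion.** The point holds as one of attribution and precision in a supportive analysis; the primary analysis is untouched. The analysis is labelled mITT but can use only infants with a reported GA, and nothing planned isolates the effect of the correction. If 50% to 80% have GA, chance alone could separate the subset and full-sample estimates by about ±0.271 to ±0.135 WAZ, or 60% to 30% of the assumed 0.45. This rests on the assumed availability, an equal true effect in infants with and without GA, SD 1.3, 354 evaluable infants and an unadjusted comparison. Selection of infants with better records could add to it by an amount that cannot be computed.

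The negative Day 1 ages follow from the formula and the entry criteria. Losing those infants is conditional on the growth table starting at age 0, and their number is unknown. The missing-GA part carries the conclusion without them.

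**What to change.** In SAP 11.5.2.4.3:

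1. Also run the 11.5.2.1 model with uncorrected WAZ in exactly the infants who contribute corrected WAZ. Report both estimates side by side and judge the effect of the GA correction from their difference, not from the contrast with the full-sample primary result.
2. State how a negative corrected age is handled, for example set to missing, as SAP 11.6.6 does for WLZ below 45 cm.
3. Compute corrected age in days as age in days minus 7 × (37 − GA), without whole-week rounding. An infant with GA 37 then keeps the same WAZ, and the difference reflects only the GA correction. As the SAP defines it, that correction also makes infants with GA above 37 older (GA 40: by 21 days).
4. Report by arm the numbers excluded for missing GA and for negative corrected age.

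The cost is one extra model run and a few lines of SAP wording. No new data are needed.
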